## 6.2.2. Cellular Immune Responses

### 6.2.2.1. Parameters

Cellular immune responses, as measured by the following assay, will be analyzed:

**Intracellular cytokine staining (ICS):** The following responses are measured:

- CD4+: IL-2, IFN- $\gamma$ , and/or TNF- $\alpha$  responses to EBOV GP.
- CD8+: IL-2, IFN- $\gamma$  and/or TNF- $\alpha$  responses to EBOV GP.

In addition, the following will be defined for the ICS:

- **Sample interpretation:** The sample positivity (interpretation) will be determined for each of the two peptide pools separately. If a sample is considered positive for at least one of the peptide pools the sample is considered positive. If a sample is positive for either IFN- $\gamma$  or IL-2, it is considered positive. A sample is considered positive when the EBOV peptide pool stimulated readout is greater than 3-fold the mock (unstimulated) readout and the mock-subtracted value is greater than the threshold (LLOQ).
- **Responder:** This will be defined based on the assay characteristics. A false positivity criterion of less than 10% for naïve samples (from non-vaccinated subjects) will be applied.

### 6.2.2.2. Data Handling Rules

For the ICS, values below the LLOQ will be imputed with half of the LLOQ (LLOQ/2). For the calculation of fold increases, values below the LLOQ will be imputed with the LLOQ.

### 6.2.2.3. Analysis Methods

The cellular immune responses will be evaluated based on the Cohort II data (see [Table 4](#)).

Summary statistics (ie, median, quartiles [Q1, Q3]) will be presented for all the continuous cellular immunogenicity outcomes at each time point. Also, the median fold increases (from Pre-dose 1 and Pre-dose 2) with the corresponding quartiles (Q1 and Q3) will be presented.

Graphical representations (on a  $\log_{10}$ -scale) will be provided using dot plots (with distinction between responders and non-responders), by vaccination schedule. Also, regimen profiles of the vaccinations schedules showing the median and the quartiles (Q1 and Q3) will be presented. Responder and positive sample interpretation rates will be summarized (ie, showing number, percentage and the corresponding exact 95% Clopper-Pearson CIs) per timepoint.

The proportions of EBOV GP-specific CD4+ and CD8+ T cells (ie, cells producing at least 1 of the 3 investigated cytokines) will also be tabulated per timepoint and shown in a pie chart. The magnitude of each cytokine subset will be shown in a bar chart. Both pie chart and bar chart will be restricted to responders.

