9.3.2. Immunogenicity Assessments

Details on sample collection and handling are provided in Section 9.5. In case of insufficient blood sample volume to perform assays, the samples will be analyzed according to the following priority ranking (ranked in order of decreasing priority): 1) core secondary endpoints, 2) core exploratory endpoints and 3) additional exploratory endpoints.

Core Immunogenicity Assessments in Cohorts II and III

Table 4 provides an overview of the core immunogenicity assessments (humoral and cellular assays) in Cohorts II and III. Blood samples for core immunogenicity assessments for the evaluation of secondary and exploratory endpoints as planned by the sponsor will be collected at the time points indicated in the Time and Events Schedule.

Blood samples (10 mL) for assessment of humoral immune responses will be obtained from all subjects in Cohorts II and III. Blood samples (40 mL) for assessment of cellular immune responses will be obtained from subjects in Cohorts II and III at selected sites with the capabilities to process PBMC (targeted at 10% of all subjects).

Table 4: Overview of Core Immunogenicity Assessments in Cohorts II and III

Sample	Core Immunogenicity Assessments (non-exhaustive)	Assays (non-exhaustive)
Serum, all subjects from Cohorts II and III	Analysis of antibodies binding to EBOV GPs Analysis of neutralizing antibodies to EBOV GPs Analysis of binding and/or neutralizing antibodies to adenovirus and/or MVA Analysis of EBOV GP, Filovirus GPs and/or TAFV NP antibody characteristics, including IgG subtyping	ELISA Virus neutralization assay Adenovirus and/or MVA ELISA and/or neutralization assay Molecular antibody characterization
PBMC, subjects from Cohorts II and III at selected sites ^a	T-cell IFN- γ responses to EBOV GP Analysis of T-cell responses to EBOV GP, Filovirus GPs and/or TAFV NP (including CD4/8, IL-2, IFN- γ , TNF- α and/or activation markers)	ELISpot ICS

ELISA: enzyme-linked immunosorbent assay; ELISpot: enzyme-linked immunospot; ICS: intracellular cytokine staining; IFN: interferon; IgG: immunoglobulin G; IL: interleukin; TNF: tumor necrosis factor

^a With the capabilities to process PBMC (targeted at 10% of all subjects).

Specific Immunogenicity Assessments in Cohort I and Additional Immunogenicity Assessments in Cohort II

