### 1.2. Trial Design

This was a randomized, observer-blind, placebo-controlled, parallel-group, multicenter, Phase 2 study to evaluate the safety, tolerability and immunogenicity of 3 heterologous prime-boost regimens using Ad26.ZEBOV at a dose of  $5 \times 10^{10}$  vp as prime and MVA-BN-Filo at a dose of  $1 \times 10^8$  infectious units (Inf U, nominal titer) as boost at a 28-, 56- or 84-day interval in healthy adult subjects in Europe (United Kingdom [UK] and France). The 3 prime-boost regimens only differed in the timing of the boost vaccination (ie, 28, 56 or 84 days after prime, respectively referred to as Groups 1, 2 and 3), while the dose of each study vaccine (Ad26.ZEBOV, MVA-BN-Filo or placebo) and the sequence of vaccination were identical. In an additional group (Group 4) in France, Ad26 vector shedding, safety, tolerability and immunogenicity following a single vaccination with Ad26.ZEBOV at a dose of  $5 \times 10^{10}$  vp was evaluated.

The subject population consisted of healthy men and women aged between 18 and 65 years (inclusive), who never received a candidate Ebola vaccine before and had no prior exposure to Ebola virus (including travel to West Africa less than 1 month prior to screening) or a diagnosis of Ebola virus disease.

At study entry, subjects were offered the option to enroll into Cohorts I (open-label), II, or III in the UK or into Cohorts II or III, or Group 4 in France. In Cohorts II and III in both countries, core immunogenicity assessments (humoral and cellular assays) were performed. In Cohort II in both countries, additional immunogenicity assessments were done. In Cohort I, plasmablast response kinetics were evaluated for the determination of the optimal sampling time points of the B-cell response as part of the additional immunogenicity assessments in Cohort II in the UK. In the UK, Cohorts I and III started in parallel, while Cohort II in the UK only started when the peak of B-cell response after prime vaccination in Cohort I was identified. In France, Cohorts II and III started in parallel (as there was no Cohort I) and were independent of Cohort I in the UK. In Group 4, immunogenicity assessments (humoral assays) and Ad26 vector shedding assessments were performed. Below is a schematic overview of the study design. For further details, see Section 3 of the CTP.

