## 1.5. Randomization and Blinding

Randomization was used to minimize bias in the assignment of subjects to vaccination schedules (groups), to increase the likelihood that known and unknown subject attributes (eg, demographic and baseline characteristics) are evenly balanced across groups, and to enhance the validity of possible statistical comparisons across groups. In addition, randomization was used to minimize bias in the assignment of subjects to study vaccine (active vaccine versus placebo).

Central randomization was implemented in this study. At baseline, subjects were randomly assigned to 1 of 3 groups in a 1:1:1 ratio in Cohorts I, II, and III. Blinding procedure were not applied to Cohort I (as all subjects received Ad26.ZEBOV and MVA-BN-Filo in an open-label fashion). Cohorts II and III were blinded. Within group, subjects were randomly assigned to Ad26.ZEBOV and MVA-BN-Filo, or placebo in a 14:1 and 10:3 ratio in Cohorts II and III, respectively, based on a computer-generated randomization schedule prepared before the start of the study under the supervision of the sponsor. Subjects in Group 4 were randomly assigned (in a blinded fashion) to Ad26.ZEBOV or placebo in a 5:1 ratio. The randomization within each group was balanced by using randomly permuted blocks and was stratified by country in Cohorts II and III. Randomization in each group (for Cohorts II and III) was further stratified by age at randomization ( $\leq 50$  years,  $> 50$  years).

In Cohorts II and III, subjects and study-site personnel were blinded to the study vaccine allocation within groups until the last subject of the study completed the 6-month post-boost visit or discontinued earlier and the clinical database was locked, except for unblinded qualified study-site personnel with primary responsibility for study vaccine preparation and dispensing, and not involved in any other study-related procedure. The study vaccines were administered by a study vaccine administrator (ie, a trained study nurse, medical doctor, or otherwise qualified health care provider who had no other study function).

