**Table 4: Cohort, Age Group Combinations and Parameters**

Study Cohort	Age Group	Analysis Parameters
Cohort I †	18-65 years	- Subject information - Safety
Group 4 ††	18-65 years	- Subject information - ELISA (units/mL) - VNA (IC 50 titers) - Safety
Cohorts II and III	18-65 years	- Subject information - ELISA (units/mL) - VNA (IC 50 titers) - ICS - Safety

Study Cohort	Age Group	Analysis Parameters
	18-50 years	- ELISA (units/mL)
	51-65 years	

† ELISA (units/mL), VNA (IC50 titers) and ICS are not assessed in Cohort I (ie, according to the CTP).

†† ICS is not assessed in Group 4 (ie, according to the CTP).

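### SAP 6.2.2.3 limits the core ICS analysis to Cohort II, against its own Table 4, SAP 1.2 and the protocol; followed as written, it omits all core Cohort III cellular data without declaring a change

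*SAP*

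**What the plan says.** SAP 6.2.2.3, the methods section for cellular responses, names one cohort: "The cellular immune responses will be evaluated based on the Cohort II data". It refers the reader to SAP Table 4.

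SAP Table 4 has a single row for Cohorts II and III, ages 18-65, whose parameters include "VNA (IC 50 titers) - ICS - Safety". Its footnotes exempt two populations from ICS: Cohort I ("ELISA (units/mL), VNA (IC 50 titers) and ICS are not assessed in Cohort I") and Group 4. Cohort III is not exempted.

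SAP 1.2 reports the conduct of the trial: "In Cohorts II and III in both countries, core immunogenicity assessments (humoral and cellular assays) were performed". Protocol 9.3.2 is the source of the samples: "Blood samples (40 mL) for assessment of cellular immune responses will be obtained from subjects in Cohorts II and III at selected sites", with a subset "targeted at 10% of all subjects". The protocol synopsis, section 3.1 and the Time and Events Schedule say the same.

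SAP section 3, on changes to the planned analysis, has two entries. Both concern the definitions of analysis sets; neither mentions cellular data or cohorts.

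**The concern.** The sentence that governs the analysis disagrees with the table it cites and with the description of where samples were taken. Two programmers working from this SAP could build different ICS populations, and nothing in the SAP says which is right.

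If the sentence prevails, three things go:

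- Cohort III's active subjects, so every ICS median, quartile and Clopper-Pearson interval rests on fewer people.
- Cohort III's placebo subjects. The cohorts were randomised to active or "placebo in a 14:1 and 10:3 ratio in Cohorts II and III, respectively", so Cohort III is far richer in placebo. Protocol 3.2 gives the placebo control the task of showing immunologic change in the absence of vaccine.
- The core Day 15 time point. In the Time and Events Schedule the core Day 15 visit applies only to Group 3 of Cohort III and includes cellular sampling. SAP Table 1 keeps a Day 15 window, and SAP 6.1 promises ICS at all available time points.

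**Working it through.** **1. Side by side.** SAP 6.2.2.3: Cohort II. SAP Table 4, SAP 1.2 and protocol 9.3.2: Cohorts II and III. SAP section 3: silent. SAP 6.2.1.3 (humoral) and section 7 (safety) both use Cohorts II and III, so 6.2.2.3 stands alone. The academic partners' fresh ICS in Cohort II does not explain it: protocol section 11 puts those data under a separate SAP, reported apart from the Clinical Study Report.

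**2. Planned allocation (SAP 1.2 table).**
- Cohort II: 3 × 84 = 252 active, 3 × 6 = 18 placebo, total 270.
- Cohort III: 3 × 80 = 240 active, 3 × 24 = 72 placebo, total 312.
- Check against protocol 11.2: 30 (Cohort I) + 270 + 312 = 612, and 252 + 240 = 492 active. Both reproduce.
- Cohort III share: 240/492 = 49% of active; 72/90 = 80% of placebo.

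**3. Reduced allocation.** The 612 was not reached. Protocol 11.2 gives Group 3 as 135 subjects, 121 active, hence 14 placebo. Assume both 135 and 121 include Group 3's 10 Cohort I subjects, as the 174 active per group in protocol Table 2 does (10 + 84 + 80). That leaves 111 active and 14 placebo in Cohorts II and III. With p2 and p3 the placebo counts and ratios 14:1 and 10:3:
- p2 + p3 = 14 and 14·p2 + (10/3)·p3 = 111
- p2 = (111 − 46.67)/10.67 = 6.0 and p3 = 8.0
- Cohort II about 84/6; Cohort III about 27/8.
- Cohort III share: 26.6/111 = 24% of active; 8.0/14 = 57% of placebo.

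If 121 excluded Cohort I, the same equations give 19% and 50%, but they need about 105 Group 3 subjects in Cohort II, where 90 were planned. The first assumption fits better.

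Assume also that Groups 1 and 2 resembled Group 3 under 1:1:1 randomisation. Then 3 × 135 = 405, and 405 + 18 (Group 4) = 423, which matches the approximate total in SAP 1.4 if that total includes Group 4.

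**4. Sampled subjects.** The 10% target dates from Amendment 4; before that it was 50%. The number actually sampled and its split by cohort are not given. With the subset spread evenly over cohorts:

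| Allocation | Sampling | Active per schedule, II only | II + III | Placebo in total, II only | II + III |
|---|---|---|---|---|---|
| Original | 10% | 8 | 16 | 1.8 | 9 |
| Reduced | 10% | 8 | 11 | 1.8 | 4.2 |
| Reduced | 50% | 42 | 56 | 9 | 21 |

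Exact 95% intervals at a 50% responder rate: 16-84% for n = 8, 25-75% for n = 16, 34-66% for n = 42, 36-64% for n = 56. For n = 11 an exact half is not possible; n = 10 gives 19-81% and n = 12 gives 21-79%.

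**5. When is most of the placebo lost?** If a fraction w of the subset comes from Cohort III, its placebo contribution is w × 3/13 against (1 − w)/15 from Cohort II. They are equal at w = (1/15)/(1/15 + 3/13) = 22.4%. Cohort III's share of the two cohorts is 312/582 = 54% as planned and 34.5/125 = 28% on the reduced figures, both above that point.

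**The case against.** **It may be only a drafting slip.** The sentence points to Table 4, which keeps Cohort III, so an analyst following the table would lose nothing. This stands: data are lost only if the sentence prevails. It does not remove the need to reconcile the two, because the SAP has no rule of precedence between them.

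**The original allocation overstates the loss.** A reader might infer that half the active and four fifths of the placebo samples would go. The documents do not support that as the size of the loss. Those shares belong to a 612-subject plan that was stopped early, and most enrolment probably preceded the 10% target. At 50% sampling on the reduced figures the effect on responder-rate precision is negligible (34-66% against 36-64%).

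**The background response does not depend on placebo.** A reader might also infer that dropping Cohort III undermines the ICS positivity rule. It does not: SAP 6.2.2.1 judges positivity against each sample's own unstimulated readout, and 6.2.2.3 takes fold increases from pre-dose values. The responder rule mentions samples from non-vaccinated people but gives no source, so dependence on trial placebo cannot be shown. What is lost is the placebo column for comparison.

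**Cohort II may have been intended.** Sampling was confined to sites able to process PBMC, and usable material may have come mainly from Cohort II. That is possible, but it would be a change from the protocol, and neither section 3 nor any other part of the SAP says so.

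**Conclusion.** The contradiction is plain on the text and the change is undeclared. Followed as written, SAP 6.2.2.3 omits all core Cohort III cellular data. Any core Day 15 ICS result goes with it, however the subset was divided, because those samples are scheduled only in Group 3 of Cohort III.

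The loss of more than half of the placebo samples is probable, not certain. It holds if Cohort III supplied more than about 22% of the subset, and the Group 3 figures put it only narrowly above half (57%).

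The loss of active subjects per schedule ranges from about 8 against 16 (original allocation, 10%) through 8 against 11 (reduced, 10%) to 42 against 56 (reduced, 50%). These figures assume an even spread of sampling over cohorts; the reduced ones also assume that Group 3's counts include 10 Cohort I subjects and that Groups 1 and 2 were similar.

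Cellular responses are exploratory and summarised descriptively. The primary safety endpoints and the secondary ELISA endpoint are untouched. What is at stake is the completeness of the cellular summaries and having one defined population for them.

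**What to change.** In SAP 6.2.2.3, replace the Cohort II restriction with pooled data from Cohorts II and III, as in Table 4 and the protocol, and add a by-cohort display if wanted. The cost is one line of text, with no new samples, visits or assays.

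If Cohort II alone was intended, for example because PBMC were available only there, move ICS in Table 4 to a Cohort II row, and declare and justify the change in section 3. In either case, report the number of subjects with cellular samples by cohort, schedule and arm, since the documents do not give it.

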## 7. SAFETY

The safety and tolerability data include the following:

- AEs collected from signing of the informed consent form (ICF) onwards until the 42-day post-boost visit.
- Serious adverse events (SAEs) and immediate reportable events (IREs) from signing of the ICF onwards until the end of the study.
- Solicited local and systemic AEs (reactogenicity) recorded during the first 8 days (including the day of the vaccination) following each vaccination.

The safety and tolerability data will be summarized based on the full analysis set. The analysis will be based on the actual dose (ie, Dose 1 and Dose 2 for the prime and boost vaccinations, respectively) that the subjects received. For example, if Dose 2 is not administered to a subject, then that subject will not be included in the analysis of AEs in the Post-dose 2 period. Focus will be on safety signals detected during the Post-dose 1 and Post-dose 2 periods, as well as the Regimen phase.

- The safety data will be evaluated based on the pooled (matching on vaccination schedules) cohorts II and III. The data will be presented separately for Cohort I and Group 4. See

[Table 4](#) for an overview.

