5. TREATMENT ALLOCATION AND BLINDING

Vaccine Schedule and Study Vaccine Allocation

Based on subject's availability and informed consent, a subject was enrolled in one of 3 cohorts at study entry. Central randomization was implemented in this study. At baseline, subjects were randomly assigned to 1 of 3 groups in a 1:1:1 ratio in Cohorts I, II, and III, and within groups randomly assigned to Ad26.ZEBOV and MVA-BN-Filo, or placebo in a 14:1 and 10:3 ratio in Cohorts II and III, respectively, based on a computer-generated randomization schedule prepared before the study by or under the supervision of the sponsor. The randomization within each group was balanced by using randomly permuted blocks and was stratified by country in Cohorts II and III. Randomization in each group (for Cohorts II and III) was stratified further according to age at randomization (≤ 50 years, > 50 years), with at least 20% (of the total of both cohorts) of subjects in the > 50 years category. Note that randomization to Group 3 was not resumed per Amendment 4 and that enrollment in the entire study will be stopped per Amendment 5. The interactive web response system (IWRS) assigned a unique code, which dictated the assignment and matching vaccination schedule for the subject. The requestor must use his or her own user identification and personal identification number when contacting the IWRS, and will then give the relevant subject details to uniquely identify the subject.

Blinding

Blinding procedures are not applicable for Cohort I (as all subjects will receive Ad26.ZEBOV and MVA-BN-Filo in an open-label fashion).

In Cohorts II and III, subjects and study-site personnel will be blinded to the study vaccine allocation within groups until the last subject of the study completes the 6-month post-boost visit or discontinues earlier and the clinical database is locked, except for unblinded qualified study-site personnel with primary responsibility for study vaccine preparation and dispensing, and not involved in any other study-related procedure. The study vaccines will be administered by a study vaccine administrator (see [Definitions of Terms](#)).

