9.1.4. Post-vaccination Phase

The subjects will come to the site at 3 and 7 days after each vaccination and also at 21 and 42 days after the boost vaccination as indicated in the [Time and Events Schedule](#). In Cohorts I and II, the subjects will come to the site for additional post-vaccination visits as indicated in the [Additional Time and Events Schedule](#). The 42-days post-boost visit (Cohorts I and II) may be replaced by a telephone call if the subject is not able to come to the site.

The subject's diary will be reviewed by study-site personnel at 3 and 7 days after each vaccination. The investigator will examine the injection site for occurrences of erythema, induration/swelling, and pain/tenderness, and will ask if itching at the injection site occurred at these visits in order to complete the relevant parts of the CRF.

Blood sampling for hematology and chemistry (fasting or non-fasting) at 7 days after each vaccination and an abbreviated, symptom-directed physical examination (as indicated by the investigator) will be performed. An ECG will be recorded at 7 days after the boost vaccination. Adverse events, serious adverse events and pregnancies will be collected and documented on the CRF, together with the information on any concomitant therapies. For reporting of IREs, refer to Section 12.3.3.

Blood samples for core immunogenicity assessments in Cohorts II and III will be collected as indicated in the [Time and Events Schedule](#) and Section 9.3.2. Blood samples for additional immunogenicity assessments in Cohort II and for specific immunogenicity assessments in Cohort I will be collected as indicated in the [Additional Time and Events Schedule](#) and Section 9.3.2.

Subjects will be instructed to contact the investigator before the next visit (ie, 6 months post-boost) if they experience any adverse event or intercurrent illness that they perceive as relevant and/or can be possibly related to study vaccine in their opinion.

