11.4. Safety Analyses

No formal statistical testing of safety data is planned. Safety data will be analyzed descriptively (including 95% confidence intervals, if applicable), by cohort and overall.

Baseline for all safety parameters will be defined as the last value before the prime vaccination.

Adverse Events (Including Reactogenicity)

The verbatim terms used in the CRF by investigators to report adverse events will be coded using the Medical Dictionary for Regulatory Activities (MedDRA). All reported adverse events (solicited local, solicited systemic, and unsolicited) will be included in the analysis. For each

adverse event, the number and percentage of subjects who experience at least 1 occurrence of the given event will be summarized by group. Summaries, listings, datasets, or subject narratives may be provided, as appropriate, for those subjects who die, who discontinue study vaccine due to an adverse event, or who experience a severe or a serious adverse event.

The analysis for solicited adverse events will be done on those subjects in the Full Analysis set for whom reactogenicity assessments are available in the database. The analysis of unsolicited adverse events will be done on the Full Analysis set.

Clinical Laboratory Tests

Laboratory abnormalities will be determined according to the toxicity grading tables, and in accordance with the normal ranges of the clinical laboratory. The most severe laboratory abnormalities following vaccination will be tabulated per regimen.

Vital Signs and Electrocardiogram

Vital signs and ECG abnormalities following vaccination will be tabulated by most severe abnormality grade.

Physical Examination

Physical examination abnormalities following vaccination will be tabulated by most severe abnormality grade.

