### 3. CHANGES TO THE PLANNED ANALYSIS

- Even in the absence of baseline immunogenicity samples, the post-baseline samples are of interest. Therefore, the immunogenicity analysis set is redefined to include subjects without baseline immunogenicity samples, provided that at least 1 post-vaccination evaluable immunogenicity sample is available for the subjects.
- Because different levels of post boost immunogenicity response are expected for different vaccination schedules, the per protocol analysis set is redefined to exclude subjects whose boost vaccination falls outside the protocol-defined window. Similar to the immunogenicity analysis set, the per protocol analysis set is also refined to include subjects without baseline immunogenicity samples.

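### Safety tables pool Cohorts II and III, a departure from the protocol that SAP 3 does not list, although the cohort mix differs between active and placebo; the rule for the safety columns is also unstated

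*SAP*

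**What the plan says.** Protocol 11.4 states: "Safety data will be analyzed descriptively (including 95% confidence intervals, if applicable), by cohort and overall". The synopsis repeats this. Protocol 11.4 adds that, for each "adverse event, the number and percentage of subjects who experience at least 1 occurrence of the given event will be summarized by group".

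SAP 7 pools: "The safety data will be evaluated based on the pooled (matching on vaccination schedules) cohorts II and III". Cohort I and Group 4 are shown separately. SAP 7.1.3 refers to "Table 4: Cohort, Age Group Combinations and Parameters" for the layout of the adverse event tables, and that table has a single combined row for Cohorts II and III that includes safety. Summaries are by vaccination schedule and period, with further tables pooled by vaccine dose.

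SAP 3 lists two changes, both to immunogenicity analysis sets. One admits subjects without a baseline sample. Under the other, "the per protocol analysis set is redefined to exclude subjects whose boost vaccination falls outside the protocol-defined window". The safety pooling is not listed.

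On how cohorts were formed, Protocol 5 says: "Based on subject's availability and informed consent, a subject was enrolled in one of 3 cohorts at study entry". On allocation, SAP 1.5 says: "Within group, subjects were randomly assigned to Ad26.ZEBOV and MVA-BN-Filo, or placebo in a 14:1 and 10:3 ratio in Cohorts II and III, respectively".

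**The concern.** Safety is the primary objective, and Protocol 3.2 gives the placebo arm the job of showing how often clinical changes occur without vaccine. A reader of the pooled tables will set the active column beside the placebo column. Cohort was not randomized and the active:placebo ratio differs between cohorts, so the two columns have different cohort mixes. Any cohort difference in background rate or in capture of adverse events would then appear partly as an active-placebo difference.

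Capture could differ somewhat. Protocol 9.1.4 says: "In Cohorts I and II, the subjects will come to the site for additional post-vaccination visits". The protocol's visit-window table gives Cohort II visits 1 and 14 days after each dose. Cohort III has only a 14-day post-prime visit, and only in Group 3. These extra contacts fall inside the SAP's Post-dose periods, which run to relative Day 29.

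There is a second, smaller gap. Protocol 3.2 says many UK subjects were boosted late. The SAP uses *schedule* for the randomized group in section 1.5, but for the actual interval in Note 4 to its Table 1 and in its Table 3. SAP 7 does not say which meaning applies to the safety columns.

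**Working it through.** The plan gives no figure for this point. The inputs are the planned counts per schedule group (active/placebo) in Protocol Table 1 and SAP 1.2: Cohort II 84/6, Cohort III 80/24.

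**Cohort II share of each pooled column**
- Active: 84/(84 + 80) = 84/164 = 0.512.
- Placebo: 6/(6 + 24) = 6/30 = 0.200.
- Gap: 0.512 - 0.200 = 0.312.
- Over all three schedules: 252/492 = 0.512 and 18/90 = 0.200, so the gap is the same.

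**Effect on the crude difference.** Let the adverse event rate be r in Cohort III and r + d in Cohort II, with no vaccine effect. The pooled active rate is r + 0.512d and the pooled placebo rate is r + 0.200d. Their difference is 0.312d. For assumed d of 5, 10 and 20 points, this is 1.6, 3.1 and 6.2 points.

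**Other cohort mixes.** SAP 1.4 reduces the study to about 423 subjects and gives no cohort split. Let w be the Cohort II share of Cohorts II and III, with allocation ratios as planned:
- active share = (14w/15) / (14w/15 + 10(1-w)/13)
- placebo share = (w/15) / (w/15 + 3(1-w)/13)
- w = 0.30: 0.342 - 0.110 = 0.232
- w = 90/194 = 0.464 (planned): 0.312
- w = 0.70: 0.739 - 0.403 = 0.336
- maximum: 0.344, near w = 0.63

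**Scale against random error**, at planned sizes and assumed rates p of 10% and 50%:
- Per group, sqrt(p(1-p)(1/164 + 1/30)) = 6.0 and 9.9 points.
- All schedules, sqrt(p(1-p)(1/492 + 1/90)) = 3.4 and 5.7 points.
- The shift equals one standard error when d is 6.0/0.312 = 19 to 9.9/0.312 = 32 points per group, or 3.4/0.312 = 11 to 5.7/0.312 = 18 points over all schedules.

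**Price of stratifying by cohort**, with Mantel-Haenszel weights and a common rate, per group:
- Stratified information: 84 x 6/90 + 80 x 24/104 = 5.60 + 18.46 = 24.06.
- Crude information: 164 x 30/194 = 25.36.
- Standard error ratio: sqrt(25.36/24.06) = 1.027.

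**Size of by-cohort placebo cells.** The exact 95% upper limit after 0 events is 1 - 0.025^(1/n):
- n = 6 (Cohort II, one group): 45.9%
- n = 24 (Cohort III, one group): 14.2%
- n = 18 (Cohort II, schedules pooled): 18.5%
- n = 72 (Cohort III, schedules pooled): 5.0%

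**Safety columns.** SAP 7 uses the full analysis set, and entry to the Post-dose 2 period depends on Dose 2 having been given, not on when. Protocol 11.4 summarizes by group. The likelier reading is therefore the assigned group, in which case late boosts sit in the assigned 28-, 56- or 84-day column. SAP 2 refers to the actual vaccine administered, which concerns product and sequence rather than interval. SAP 5.1 lists assigned and actual regimen per subject and tabulates entry into each analysis period. Subjects without Dose 2 have no Post-dose 2 period, so the boosted/unboosted split is already covered. Only the on-time/late split is missing.

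**The case against.** The case for leaving the plan alone is substantial. Safety is descriptive, no formal test is planned and the SAP specifies no active-minus-placebo difference, so the 0.31 factor applies to a comparison that the reader makes rather than one in the plan. The multiplier d is unknown, and nothing in the documents suggests a gap large enough to rival sampling error. Both cohorts receive the same vaccines and doses, and solicited events use the same diary and the same 3- and 7-day reviews. Demographics are planned for each cohort (SAP 5.3), so the actual mix will be visible. By-cohort placebo cells are very small.

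All of this limits the size of the point. It does not explain why the protocol's by-cohort presentation was dropped, or why SAP 3 is silent. SAP 2.2 even pools sites and countries by matching on cohort as well as schedule, which sits badly with SAP 7.

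Three stronger readings are tempting and not supported:
- *The pooled tables are biased.* The documents give no cohort difference in rates, so only the potential for bias is shown.
- *The telephone option for Cohort II's 42-day post-boost visit makes capture unequal.* The main Post-dose 2 summaries end at relative Day 29 and every cohort has a 21-day post-boost visit. The option therefore touches about the last week of that period, and only for subjects who cannot attend. It could matter more in the entire-period tables, such as Grade 3 events.
- *The by-schedule Post-dose 2 tables definitely mix on-time and late boosts.* That follows only if columns are by assigned group, which the SAP does not say.

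**Conclusion.** The point holds as an undeclared departure from the protocol's safety presentation that removes the only planned view in which a Cohort II versus III difference could be seen. At the planned mix the crude active-minus-placebo difference shifts by 0.31 x d. Over an assumed Cohort II share of 30% to 70% the factor runs from 0.23 to 0.34. These figures assume the allocation ratios were achieved, and the shift is zero if d is zero. It should be fixed because safety is primary and the remedy restores the protocol's own plan.

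The column question is secondary. It is an undefined rule, not a breach: neither document promises safety by actual interval. No size can be given, because neither the number of late boosts nor their event rates are stated.

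**What to change.** Main changes:
- Add safety tables for Cohort II and for Cohort III beside the pooled ones, pooling schedules within cohort because the placebo cells are small.
- Stratify any descriptive active-placebo comparison by cohort.
- List the Cohort II/III pooling in SAP 3, with a reason.

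Secondary changes:
- State in SAP 7 whether safety columns follow the assigned group or the actual interval.
- Show, per assigned group, how many boosted subjects were boosted on time and how many late.

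Optional: supplementary Post-dose 2 tables by groups A to D of SAP Table 3. These groups are not randomized and are tied to country and calendar time. Their windows are about 28 days wide against a protocol boost window of plus or minus 1 day, so A to C would still mix intervals.

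The cost is SAP wording and extra descriptive output. Cohort is already recorded and groups A to D are already defined for immunogenicity. Stratifying costs about 2.7% in standard error at planned sizes. The by-cohort tables will be imprecise, and more so than the planned counts imply because enrollment stopped early.
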